Protocol Number: ^{18}F -AV-1451-A14

Clinical Evaluation of ^{18}F -AV-1451

Date and Version:

[figure not shown]
05Sep2014 Amendment 1

Name of Compound:

^{18}F -AV-1451 ([^{18}F]T807)

Sponsor:

Avid Radiopharmaceuticals
Philadelphia, Pennsylvania USA

CONFIDENTIAL

This material is the property of Avid Radiopharmaceuticals (Avid). The information is confidential and is to be used only in connection with matters authorized by Avid and no part of it is to be disclosed to others without prior written permission from Avid.

Sponsor: Avid Radiopharmaceuticals	Name of Compound: ¹⁸ F-AV-1451([F-18]T807)	Active Ingredient(s): 7-(6-[F-18]fluoropyridin-3-yl)-5H-pyrido[4,3-b]indole
Title of Study: ¹⁸ F-AV-1451-A14 “Clinical Evaluation of ¹⁸ F-AV-1451”		
Planned number of subjects (Enrolled): Approximately 250 subjects including healthy controls and subjects at risk for tau accumulation as defined by the site’s companion protocol.		
Name of compound: ¹⁸ F-AV-1451([F-18]T807) Dose: Up to a target dose 370 MBq (10 mCi) Route of Administration: Intravenous (IV) bolus		
Study Phase: II		
Study Centers: Approximately 10 centers in the United States and Canada		
Trial Objectives: The primary objectives of this study are: 
 • Provide standardized conditions for ¹⁸F-AV-1451 use, data collection, and analysis to facilitate evaluation of subject’s tau burden. • To expand the ¹⁸F-AV-1451 safety database. 		
Eligibility: Subjects should meet inclusion and exclusion criteria for the companion protocol, and in addition: Subjects who meet all of the following criteria are eligible to enroll in this study: 
 1. Male or female subjects at least 18 years of age; 2. Subjects who sign an IRB approved informed consent prior to any study procedures. Where subjects are deemed incapable of informed consent, a legally authorized representative may provide consent, with the subject’s documented assent; 3. Subjects who have historical volumetric brain MRI images obtained as part of the site’s companion protocol available for submission to Avid; and 4. Subjects who in the opinion of the investigator can tolerate the PET scan procedures. 		

Sponsor: Avid Radiopharmaceuticals	Name of Compound: ¹⁸ F-AV-1451([F-18]T807)	Active Ingredient(s): 7-(6-[F-18]fluoropyridin-3-yl)-5H-pyrido[4,3-b]indole
--	---	---

Subjects will be excluded from enrollment if they:

1. Have clinically significant cardiac, hepatic, renal, pulmonary, metabolic, or endocrine disturbances as indicated by history, which in the opinion of the investigator might pose a potential safety risk to the subject;
2. Have either: 1) Screening ECG with QTc > 450 msec if male or QTc > 470 msec if female; or 2) A history of additional risk factors for Torsades de Pointes (TdP) (e.g., hypokalemia, family history of Long QT syndrome) or are taking drugs that are known to cause QT-prolongation (a list of prohibited and discouraged medications is provided by the Sponsor); Patients with a prolonged QTc interval in the setting of intraventricular conduction block (examples RBBB or LBBB), may be enrolled with sponsor approval;
3. Have a history of drug or alcohol dependence within the last year, or prior prolonged history of dependence unless approved by the sponsor;
4. Are females of childbearing potential who are not surgically sterile, not refraining from sexual activity or not using reliable methods of contraception. Females of childbearing potential must not be pregnant (negative serum or urine β-HCG at the time of screening and negative serum or urine β-HCG on imaging day) or breastfeeding at screening. Females must agree to avoid becoming pregnant, and both females and males must agree to refrain from sexual activity or to use reliable contraceptive methods for 90 days following administration of ¹⁸F-AV-1451 Injection;
5. Have a history of relevant severe drug allergy or hypersensitivity (Relevant severe drug allergies should be determined by the PI, and any questions about a subject's eligibility can be directed to Avid. If a subject has a history of severe drug allergies, it may be dangerous for them to participate in a study);
6. Are patients who have received an investigational medication under an FDA IND protocol within 30 days prior to the planned imaging session for this study, with the exception of medications allowed in the companion study and approval from sponsor. Additionally, the time between the last dose of the previous experimental medication and imaging must be at least equal to 5 times the terminal half-life of the previous experimental medication;
7. Are patients with current clinically significant unstable medical comorbidities, as indicated by history or physical exam that pose a potential safety risk to the subject;
8. Are patients who have received a radiopharmaceutical for imaging or therapy within the past 24 hours prior to the imaging session for this study. If another radiotracer is required in the companion protocol, patients may be able to receive a radiopharmaceutical for imaging or therapy within the 24 hours prior to the imaging session with prior sponsor approval;
9. Are patients who, in the opinion of the investigator, are otherwise unsuitable for a study of this type.

Sponsor: Avid Radiopharmaceuticals	Name of Compound: ¹⁸ F-AV-1451([F-18]T807)	Active Ingredient(s): 7-(6-[F-18]fluoropyridin-3-yl)-5H-pyrido[4,3-b]indole
Study Design: Study ¹⁸ F-AV-1451-A14 is designed to expand the database of ¹⁸ F-AV-1451 safety and tau binding as measured by PET imaging, and to provide standardized conditions for tau use, data collection and analysis to facilitate companion studies including, but not limited to, longitudinal studies of aging, depression, and traumatic brain injury. Approximately 250 subjects will be studied under this protocol.		
Assessments and Endpoints: Screening: Screening assessments may take place over several days and will include collection of demographic information, a medical assessment for eligibility, ECG, a brief cognitive assessment (e.g. MMSE), and a traumatic brain injury questionnaire. ¹⁸F-AV-1451 PET Imaging Visit: Subjects who qualify for the study will come to the imaging center at a later date and will have a catheter(s) placed for i.v. administration of ¹⁸ F-AV-1451. Vital signs will be taken in a supine position immediately prior to administration of ¹⁸ F-AV-1451 (within 30 minutes prior to injection) and at the completion of imaging prior to subject discharge. Subjects will receive up to a target dose of 370 mBq as a single i.v. bolus of ¹⁸ F-AV-1451. A 20 minute dynamic image starting approximately 80 minutes post injection will be obtained. With sponsor approval sites may elect an alternative imaging protocol (i.e. different duration or start time) with additional time points. All datasets will be submitted to the sponsor for analysis. Adverse events will be continuously monitored during the imaging session. Subjects who experience any adverse event will not be discharged until the event has resolved or stabilized. Repeat Imaging: Longitudinal imaging studies may be conducted under protocol ¹⁸ F-AV-1451-A14, with prior sponsor approval. In these studies, subjects may have up to two imaging sessions within a 12 month time-frame. If the second scan is obtained more than 3 months after the previous scan, then the MMSE should be repeated and updates to the OSU-TBI, medical history, and concomitant medications will be collected. Procedures for each imaging day will be identical to those described above. Follow-Up Phone Call: A follow-up phone call to the subject, or designated decision maker, will be conducted between 2 or 3 business days after imaging day, but not before 48 hours post-injection, to confirm subject well-being and to collect information about any new adverse events. If both of these days are not business days, the follow-up phone call can occur the following business day. Details of additional assessments that will be performed at each visit are detailed in Section 7.1.		

Sponsor: Avid Radiopharmaceuticals	Name of Compound: ¹⁸ F-AV-1451([F-18]T807)	Active Ingredient(s): 7-(6-[F-18]fluoropyridin-3-yl)-5H-pyrido[4,3-b]indole

Adverse Event (AE)	Any untoward medical occurrence in a subject or clinical investigation subject administered a pharmaceutical product and that does not necessarily have a causal relationship with this treatment.
Audit	A systematic and independent examination of the trial-related activities and documents to determine whether the evaluated trial-related activities were conducted, and the data were recorded, analyzed, and accurately reported according to the protocol, applicable standard operating procedures (SOPs), good clinical practice (GCP), and the applicable regulatory requirement(s).
Case Report Form (CRF) and electronic Case Report Form (eCRF)	A printed or electronic form for recording study participants' data during a clinical study, as required by the protocol.
CNS	Central Nervous System
CRO	Contract Research Organization: A person or organization (commercial, academic, or other) contracted by the sponsor to perform one or more of the sponsor's trial-related duties and functions.
CT	Computed Tomography
ECG	Electrocardiogram
Efficacy	Efficacy is the ability of a treatment to achieve a beneficial intended result.
FDA	US Food and Drug Administration
FDG	¹⁸ F - Fluorodeoxyglucose
GCP	Good Clinical Practice
ICH	International Conference on Harmonization

Institutional Review Board /Independent Ethics Committee	A board or committee (institutional, regional, or national) composed of medical and nonmedical members whose responsibility is to verify that the safety, welfare and human rights of the subjects participating in a clinical study are protected.
Investigator	A person responsible for the conduct of the clinical trial at a trial site. If a trial is conducted by a team of individuals at a trial site, the investigator is the responsible leader of the team and may be called the principal investigator.
IV	Intravenous
MBq	Megabecquerel
mCi	Millicurie
MHD	Maximum Human Dose
MMSE	Mini Mental State Examination
MRI	Magnetic Resonance Imaging
NOAEL	No Observable Adverse Effect Level
OSU TBI-ID	Ohio State University Traumatic Brain Injury Identification Method (OSU TBI-ID)
PET	Positron Emission Tomography
RBT	Repetitive Brain Trauma
SUVR	Standard Uptake Value Ratio
TBI	Traumatic Brain Injury

1. INTRODUCTION

¹⁸F-AV-1451 (originally named [F-18]T807 by Siemens Molecular Imaging Biomarker Research group) has been developed as a positron emitting radiopharmaceutical for *in vivo* imaging of tau protein aggregates (Xia et al., 2013). Autoradiography results using tissue sections from human brains showed a strong signal in the grey matter of cortical slices from tau positive brains but weak or no binding in tau negative, A β positive, or tau and A β negative tissue. Scatchard analysis based on this heterogeneous autoradiography assay yielded an estimated K_d of 15nM. A saturation binding experiment using purified Paired Helical Fragment-Tau isolated brains of AD patients yielded a K_d value of 0.7 nM.

AV-1451 was assessed in competitive binding assays against a panel of 72 of the most common central nervous system (CNS) targets and no clinically relevant inhibition was seen. AV-1451 was positive in the *in vitro* hERG assay, albeit at a concentration more than 40-fold the maximum theoretical AV-1451 plasma concentration. Additionally, *in vivo* cardiovascular safety pharmacology assessments in dogs showed no evidence of QT prolongation at doses up to 50x the intended maximum human dose (MHD). Nonetheless, until sufficient human cardiovascular safety data are available, initial clinical studies will exclude subjects with a history of risk factors for Torsades de Pointes and subjects taking drugs known to prolong the QT interval.

In vivo safety pharmacology studies were also conducted in rats to determine potential effects on the CNS and respiratory systems. In these studies no clinically relevant effects were reported at doses exceeding 100x the intended MHD. Additionally, non-radioactive AV-1451 has been tested in single and repeat dose toxicology studies in rat and dog species. In each of these studies the no observable adverse effect levels (NOAELs) were the highest doses tested (150x MHD for single, 50x MHD for repeat).

Potential genotoxicity of non-radioactive AV-1451 was tested in both *in vitro* and *in vivo* assays. In the *in vitro* assays, AV-1451 tested positive for potential genotoxicity. However, in the *in vivo* rat micronucleus assay at doses up to 750x MHD (scaled allometrically), AV-1451 showed no evidence of genotoxicity. The different results in the *in vitro* genotoxicity assays and the *in vivo* micronucleus study are likely related to differences in the exposure conditions encountered by the target cells in the different test systems. *In vivo*, AV-1451 is cleared rapidly; however, the *in vitro* experiments employ static, prolonged exposure of cells to high concentrations of the test article. While the *in vitro* data show the potential for genotoxicity, the *in vivo* data provide assurance that genotoxicity is unlikely to occur at clinically-relevant doses for human diagnostic studies.

Human dosimetry has been obtained in nine subjects. Generally, the radiotracer distribution was consistent among the subjects and showed rapid hepatobiliary clearance. There were three organs that received estimated doses higher than 0.05 mSv/MBq. The organ that received the largest estimated dose was the upper large intestinal wall (0.0962 \pm 0.0134 mSv/MBq), followed by the small intestine and the liver. The Effective Dose was 0.0241 \pm 0.0016 mSv/MBq. This results in an estimated Effective Dose of 8.92 mSv for an anticipated 370 MBq (10 mCi) injection and is comparable to the effective dose of approved ¹⁸F-labeled compounds such as fluorodeoxyglucose (FDG) and florbetapir F 18 injection.

^{18}F -AV-1451 may be useful as a marker of tau pathology in patients with AD and other neurodegenerative disorders (Figures 1 and 2). Several preliminary studies using ^{18}F -AV-1451 have been completed (e.g., Chien et al., 2013).

The present study is designed to expand the database of ^{18}F -AV-1451 safety and tau binding as measured by PET imaging, and to provide standardized conditions for tau use, data collection, and analysis to facilitate companion studies including, but not limited to, longitudinal studies of aging, depression, and traumatic brain injury.

[figure not shown]

Figure 1: [REDACTED] control subject (MMSE = 29)

[figure not shown]

Figure 2: [REDACTED] AD subject (MMSE = 18)

2. TRIAL OBJECTIVES

The primary objectives of this study are:

[figure not shown]
- Provide standardized conditions for ^{18}F -AV-1451 use, data collection and analysis to facilitate evaluation of subject's tau burden.
- To expand the ^{18}F -AV-1451 safety database.

4. TEST DRUG AND CONTROL AGENTS

4.1. Descriptive Name: ^{18}F AV-1451

7-(6-[^{18}F]fluoropyridin-3-yl)-5H-pyrido[4,3-b]indole

MW = 262.27 amu

4.2. Radioactive Labeling

The compound is labeled with [^{18}F] fluorine that decays by positron (β^+) emission and has a half-life of 109.77 min. The principal photons useful for diagnostic imaging are the 511 keV gamma photons, resulting from the interaction of the emitted positron with an electron.

4.3. Decay Characteristics

The time course of radioactive decay for Fluorine [^{18}F] is shown below

Min.	Fraction Remaining
0	1.000
30	0.827
60	0.685
90	0.567
120	0.469
150	0.388
180	0.321
210	0.266
240	0.220

Physical decay chart for Fluorine [^{18}F]. Half-life = 109.77 min.

4.4. Formulation and Dose ^{18}F -AV-1451 Injection

^{18}F -AV-1451 Injection is a clear solution containing ^{18}F -AV-1451 (drug substance) formulated for intravenous bolus administration. Depending on the manufacturer, ^{18}F -AV-1451 Injection will be formulated in either:

- aqueous 21 mM sodium phosphate solution containing up to 10% (v/v) ethanol, or
- a solution containing 10% (v/v) ethanol, USP in 0.9% sodium chloride injection, USP.

Drug product of either formulation is manufactured to meet one common set of specifications.

The expiration time and date of ^{18}F -AV-1451 Injection are provided on the outer label of each dose based on specific activity or strength. ^{18}F -AV-1451 Injection should be stored at room temperature.

4.5. Packaging ^{18}F -AV-1451 Injection

Each package of ^{18}F -AV-1451 Injection includes a sterile apyrogenic sealed glass vial or sterile apyrogenic syringe containing ^{18}F -AV-1451 Injection, a surrounding protective lead shield canister, and an outside delivery case.

4.6. Storage and Handling $^{18}\text{F-AV-1451}$ Injection

$^{18}\text{F-AV-1451}$ Injection is stored at room temperature. $^{18}\text{F-AV-1451}$ Injection should be stored within the original container or equivalent radiation shielding. $^{18}\text{F-AV-1451}$ Injection must not be diluted.

5. INVESTIGATIONAL PLAN

5.1. Overall Design and Plan of Trial

Protocol $^{18}\text{F-AV-1451-A14}$ is designed to expand the database of $^{18}\text{F-AV-1451}$ safety and tau binding as measured by PET imaging, and to provide standardized conditions for $^{18}\text{F-AV-1451}$ use, data collection and analysis to facilitate companion studies looking at tauopathies. Approximately 250 subjects will be studied under this protocol.

Screening assessments may take place over several days and will include the collection of demographic information, a medical assessment for eligibility, ECG, a brief cognitive interview, including an MMSE, and a brain injury questionnaire.

Subjects who qualify for the study will come to the imaging center at a later date and will have catheter(s) placed for i.v. administration of $^{18}\text{F-AV-1451}$. Vital signs will be taken in a supine position immediately prior to administration of $^{18}\text{F-AV-1451}$ (within 30 minutes prior to injection) and at the completion of imaging prior to discharge. Subjects will receive a single i.v. bolus of $^{18}\text{F-AV-1451}$, a 20 minute dynamic scan will be obtained starting approximately 80 minutes post injection. With sponsor approval sites may elect an alternative imaging protocol with additional time points. All datasets will be submitted to the sponsor for analysis.

Adverse events will be continuously monitored during the imaging session. Subjects who experience any adverse event will not be discharged until the event has resolved or stabilized.

A follow-up phone call to the subject, or designated decision maker, will be conducted between 2 or 3 business days after imaging day, but not before 48 hours post-injection, to confirm subject well-being and to collect information about any new adverse events. If both of these days are not business days, the follow-up phone call can occur the following business day.

Longitudinal imaging studies may be conducted under protocol $^{18}\text{F-AV-1451-A14}$, with prior sponsor approval. In these studies subjects may have up to two imaging sessions within a 12 month time-frame. If the second scan is obtained more than 3 months after the previous scan then the MMSE should be repeated and updates to the OSU-TBI, medical history, and concomitant medications will be collected. Procedures for each imaging day will be identical to those described above. Adverse events will not be collected during the time between the first follow-up phone call and the second imaging session, but will be added to the medical history if clinically relevant.

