7.7.2. Adverse Event Definitions

Adverse Events

An adverse event is any undesirable experience occurring to a subject during a clinical trial, whether or not considered related to the study drug.

For reporting purposes, Avid will distinguish among pre-existing conditions, trial-emergent adverse events and treatment-emergent adverse events.

Pre-existing conditions (i.e., undesirable experiences, signs or symptoms that begin prior to the Screening Visit) will be recorded on the medical history eCRF pages. During the study, site personnel will record any change in the condition(s) and occurrence and nature of any AEs. Signs and symptoms that are believed to be due to the pre-existing condition under study (started prior to dose of study medication) do not have to be recorded in the AEs section of the eCRF, unless there is an increasing in frequency and severity.

Trial-emergent adverse events are undesirable experiences, signs or symptoms that begin, or worsen in intensity or frequency, after the informed consent, and prior to administration of study drug (^{18}F -AV-1451) at the imaging visit. These will be recorded on the adverse event eCRFs.

Treatment-emergent adverse events are undesirable experiences, signs, or symptoms associated with the use of a study drugs. For the purposes of this study an adverse event will be considered associated with the use of ^{18}F -AV-1451 if it begins or worsens in intensity or frequency within 48 hours after the administration of ^{18}F -AV-1451. Adverse experiences that occur after administration of study drug but outside the 48 hour reporting window will not be reported unless the investigator believes they are attributable to the drug.

The end of study for the purpose of adverse event reporting is defined as 48 hours after the administration of ^{18}F -AV-1451 Injection.

Serious Adverse Event (SAE)

A SAE is an AE that results in one of the following outcomes or constitutes one of the following events:

- Death;
- Initial or prolonged inpatient hospitalization (other than that required by protocol; “social hospitalization” or any hospitalization for non-medical reasons does not constitute a SAE);
- A life-threatening experience (that is, immediate risk of dying);
- Persistent or significant disability/incapacity;

- Congenital anomaly/birth defect;
- Considered significant by the investigator for any other reason.

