7.7.4. Reporting of Serious Adverse Events

Study site personnel must alert Eli Lilly or its designee of any SAE within 24 hours of their awareness of the event via a sponsor-approved method. Alerts issued via telephone are to be immediately followed with official notification on study-specific SAE forms.

Serious adverse events occurring after a subject receive a dose of study drug will be collected until 48 hours after the dosing of the study drug, regardless of the investigator's opinion of causation. Therefore, SAEs that occur later than 48 hours after the dosing of the study drug are not required to be reported unless the investigator feels the events were related to either study drug or a protocol procedure.

If a patient experiences a SAE after signing informed consent, but prior to receiving study drug, the event will NOT be reported unless the investigator feels the event may have been caused by a protocol procedure. Previously planned (prior to signing the ICF) surgeries should not be reported as SAEs unless the underlying medical condition has worsened during the course of the study.

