8.5.2 Treatment Emergent Adverse Events

A summary of TEAEs will be reported in the tables including number of all TEAEs and number of subjects who experienced at least one TEAE. The summary of TEAEs will be broken down further in descending frequency by SOC and PT, and by PT only in separate tables. A subject will be counted once if the subject reported one or more events in a given level of summarization.

All AEs (regardless of treatment emergence) will be presented in a listing.

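### Protocol 5.1 stops adverse-event collection between scans without the exceptions for late attributed events that 7.7.2 and 7.7.4 state

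*Protocol*

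**What the plan says.** Repeat imaging is optional and needs sponsor approval. Under protocol section 5.1, "subjects may have up to two imaging sessions within a 12 month time-frame". For the time between the two, the same section says "Adverse events will not be collected during the time between the first follow-up phone call and the second imaging session", and the sentence ends "but will be added to the medical history if clinically relevant". Neither the synopsis, protocol 7.1.4 nor SAP 4.1.4 repeats this rule, although all three describe repeat imaging.

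Other sections also deal with late events:

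- Protocol 7.7.2, on adverse events after dosing: those "outside the 48 hour reporting window will not be reported unless the investigator believes they are attributable to the drug". The next paragraph ends the study, for adverse-event reporting, 48 hours after administration.
- Protocol 7.7.4, on serious events more than 48 hours after dosing: they need not be reported "unless the investigator feels the events were related to either study drug or a protocol procedure".
- Protocol 10.7: every adverse event met during the trial goes on the eCRF, related or not, and serious events are notified within 24 hours.
- SAP 8.5.2: "All AEs (regardless of treatment emergence) will be presented in a listing".

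**The concern.** The exceptions in 7.7.2 and 7.7.4 have no end date and do not leave out subjects awaiting a second scan. Section 5.1 has no exception and names a different destination for the record. For a late event that the investigator attributes to the drug, a site therefore has two instructions that cannot both be followed as written.

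Expanding the safety database is one of the study's two primary objectives. Medical history is a poor substitute for an adverse-event record. Section 7.7.2 uses it for conditions that began before the Screening Visit. Adverse events require relatedness and severity assessments (7.7.2), whereas the SAP plans only a coded listing for medical history (8.3.2). For a related serious event, the 24-hour alert in 7.7.4 is also at stake.

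**Working it through.** No figure in the plan bears on this point, so the check compares the rules and their timing.

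**Timing.** The gap opens at the first follow-up call, which takes place "but not before 48 hours post-injection". It closes at the second imaging session, within 12 months. The gap therefore lies wholly outside the 48-hour window and can last at most just under 12 months. Inside it, only the late-event rules apply.

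**Rules by type of event in the gap.**

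| Event | Section 5.1 | Sections 7.7.2 and 7.7.4 | Agree? |
|---|---|---|---|
| Non-serious, not attributed to the drug | Not collected; medical history if relevant | Not reported (7.7.2) | Yes |
| Non-serious, attributed to the drug | Same | Reported (7.7.2) | **No** |
| Non-serious, related only to a procedure | Same | Not reported; the 7.7.2 exception covers the drug only | Yes |
| Serious, unrelated | Same | Not required (7.7.4) | Yes |
| Serious, related to drug or procedure | Same | Reported, within 24 hours of awareness (7.7.4) | **No** |

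The disagreement is confined to two rows, which are the events that 7.7.2 and 7.7.4 still want at that stage. Section 10.7 would put all five rows on the eCRF if the gap counts as part of the trial. The protocol leaves that unclear, because 7.7.2 ends adverse-event reporting at 48 hours.

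**The fallback record.** Protocol 5.1 and 7.1.4 schedule a medical-history update only when the second scan comes more than 3 months after the first. Eligibility must be met again at the second session (5.4), but for shorter intervals no history update is scheduled.

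**Consequence in the analysis.**

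- SAP 6.6.2 defines a treatment-emergent event by the 48-hour window, with no exception for later attributed events. An event in the gap enters no treatment-emergent table, whichever form it is recorded on.
- The all-events listing in SAP 8.5.2 is the planned output that would show the event as an adverse event. An event held only as medical history would appear in the 8.3.2 listing instead.

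**Size.** SAP 4.4 gives approximately 179 dosed subjects. Repeat-imaging subjects are some unstated part of these, and no rate of late attributed events is given. A count cannot be derived.

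**The case against.** The best defence is that 5.1 only describes the end of routine collection. Section 7.7.4 uses the same verb: serious events are collected until 48 hours, yet related later ones remain reportable. In 7.7.2 the attribution exception likewise sits beside a 48-hour end of reporting. On that reading 5.1 is an overview sentence that overrides nothing, and 7.7, 7.7.2, 7.7.4 and 10.7 continue to bind every site.

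This is a fair reading and may be what the sponsor intended. It does not fully reconcile the text. Section 5.1 goes beyond ending collection, because it says where the events go, and that place is neither the adverse-event eCRF nor the serious-event form. It is also the rule written specifically for repeat-scan subjects, and no order of precedence is stated.

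The defence does limit the consequences. Three stronger readings are tempting, and the documents support none of them:

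- *Every attributed event in the gap will be misfiled.* That requires sites to apply one sentence of 5.1 and disregard 7.7.2, 7.7.4 and 10.7.
- *Events are lost in twice-exposed subjects, who are therefore less well ascertained than one-scan subjects.* The gap precedes the second injection, so only one exposure has occurred. One-scan subjects have no scheduled contact after the follow-up call. Repeat-scan subjects return and see a physician before dosing, so they have more opportunity for detection. What may differ is the form on which the event is recorded.
- *The treatment-emergent summaries are biased.* They use the 48-hour window alone and would not change. Events within 48 hours of either injection are unaffected.

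**Conclusion.** The inconsistency is real and should be corrected, but its reach is small. Section 5.1 conflicts with 7.7.2 for late drug-attributed adverse events and with 7.7.4 for late serious events related to drug or procedure. It also sits uneasily with the general rule in 10.7. Followed literally in a repeat-imaging subject, it could put such an event in medical history, bypass the serious-event report and keep the event out of the adverse-event listing. No treatment-emergent table changes.

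This conclusion assumes that the exceptions in 7.7.2 and 7.7.4 apply to subjects awaiting a second scan; nothing in the documents says otherwise. It does not assume that any such event occurred.

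**What to change.** **Protocol 5.1.** Reconcile the sentence with 7.7.2, 7.7.4 and 10.7 by making it subject to the exceptions already stated: adverse events attributed to the drug (7.7.2), and serious events related to study drug or a protocol procedure (7.7.4). These go on the adverse-event eCRF and, where serious, on the serious-event form as well. The exception should go no further. Extending it to non-serious events related only to a procedure would be a new rule, since 7.7.2 does not cover them.

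**SAP 8.5.2.** State that between-scan events meeting those exceptions appear in the adverse-event listing, flagged as outside the 48-hour window. Include any found among medical-history entries with onset after the first injection. The SAP already describes dosing in the past tense, so the protocol change may come too late to alter collection. The SAP sentence can still recover events already recorded as medical history.

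**Cost.** One sentence in each document, a review of medical-history onset dates in repeat-imaging subjects, and a flag in one listing. No summary table or denominator changes.
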